### **Secondary Efficacy Endpoints**

Descriptive statistics for the CGI-S score and change from baseline in CGI-S score will be presented by treatment group and visit.

Finally, the dichotomized endpoints of response and remission will be presented as the percentage of subjects meeting the response or remission criteria at Visit 8/ET (Week 6/ET). Both will be scored as 1 for Response/Remission and 0 for non-Response/Remission. Response is defined as:

	A $\geq$ 30% reduction from Baseline in ADHD-RS-5 total score.
	Improved on the CGI-I which includes the categories of 1 (very much improved) and 2 (much improved).
	Both a $\geq$ 30% reduction in ADHD-RS-5 total score and improved (1 [very much improved] and 2 [much improved] on the CGI-I.
Remis	sion is defined as follows:
	An ADHD-RS-5 total score ≤18.
	A CGI-I of 1 (very much improved).
	Both an ADHD-RS-5 total score ≤18 and a CGI-I of 1 (very much improved).
Explo	ratory Efficacy Endnoints

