### 14.3.4 Efficacy Analyses

All efficacy measures will be described with standard summary statistics. Continuous variables will be summarized by N, the mean and standard deviation, and categorical variables will be summarized by the number and percent of subjects in each category. The analysis of response rate will be performed after randomized subjects have completed their final visit. This will be calculated as the proportion of the Full Analysis Set population who achieve responder status. The response rate will be expressed as a percentage with an accompanying 95% CI. Comparisons of dichotomized responses between treatment groups will be based on odds ratios and associated 95% CIs resulting from the logistic regression model.

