2.1.2 Secondary objectives

The key secondary objective of each part of this study will be:

• To evaluate the efficacy of AEVI-001 compared with placebo using a global clinical measure of improvement, the Clinical Global Impression – Improvement (CGI-I) at Visit 8/Early Termination (ET) (Week 6/ET).

Additional secondary objectives of each part of the study include:

- To evaluate AEVI-001 compared with placebo on response at Visit 8/ET (Week 6/ET), based on the following parameters:
 - A \geq 30% reduction from baseline in ADHD-RS-5 total score.
 - Improved on the CGI-I which includes the categories of 1 (very much improved) and 2 (much improved).
 - Both a ≥30% reduction in ADHD-RS-5 total score and improved (1 [very much improved] and 2 [much improved]) on the CGI-I.
- To evaluate AEVI-001 compared with placebo on remission at Visit 8/ET (Week 6/ET), based on the following parameters:
 - An ADHD-RS-5 total score ≤ 18 .
 - A CGI-I of 1 (very much improved).
 - Both an ADHD-RS-5 total score \leq 18 and a CGI-I of 1 (very much improved).
- To evaluate the efficacy of AEVI-001 compared with placebo using a global clinical measure of severity, the Clinical Global Impression Severity (CGI-S) at Visit 8 (Week 6).

• To evaluate the safety and tolerability of AEVI-001 compared with placebo based on occurrence of treatmentemergent adverse events (TEAEs), vital signs, clinical laboratory results, electrocardiogram (ECG) results, and the Columbia-Suicide Severity Rating Scale (C-SSRS).

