4.7.1.3 ADHD-RS-5 remission

An indicator of ADHD-RS-5 remission will be calculated at each post-baseline timepoint as:

- IF the ADHD-RS-5 total score is \leq 18, THEN set the ADHD-RS-5 remission indicator equal to 1.
- IF the ADHD-RS-5 total score is >18, THEN set the ADHD-RS-5 remission indicator equal to 0.

In addition to deriving ADHD-RS-5 remission at each timepoint, an LOCF ADHD-RS-5 remission indicator will be calculated.

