5.4 Secondary efficacy analyses

Logistic regression methods will be used for the analysis of the LOCF ADHD-RS-5 response indicator using the full analysis set. The logistic regression model will include terms for age stratum, treatment group, and baseline ADHD-RS-5 total score. The comparison of interest will be the difference between the AEVI-001 and placebo treatment groups at end-of-treatment. Model based point estimates (i.e., odds ratios), 95% confidence intervals, and p-value will be reported.

Similar logistic regression models will be used for the LOCF CGI-I remission, LOCF combined ADHD-RS-5/CGI-I response, and LOCF combined ADHD-RS-5/CGI-I remission indicators using the full analysis set. For the CGI-I response/remission analyses, baseline CGI-S score will be included in the model. For the combined response/remission analyses, baseline ADHD-RS-5 total and CGI-S scores will be included in the model.

MMRM methods similar to those described in Section 5.3 will be used for the analysis of the following change from baseline values: ADHD-RS-5 inattention subscale, ADHD-RS-5 hyperactivity–impulsivity subscale, and CGI-S, Conners 3-P(S) inattention subscale, Conners 3-P(S) hyperactivity–impulsivity subscale, Conners 3-P(S) learning problems subscale, Conners 3-P(S) executive function subscale, Conners 3-P(S) aggression subscale, and Conners 3-P(S) peer relations subscale. For each model, the baseline score of the respective subscale used in the model will be used as a covariate. For the models including Conners 3-P(S) subscale scores, a heterogeneous first order autoregressive (i.e., TYPE = ARH(1)) covariance structure will be used in cases of convergence problems. As with the primary efficacy analysis, the comparison of interest for each model will be the difference between the AEVI-001 and placebo treatment groups at Week 6. Model based point estimates (i.e., LS means for each treatment group and the treatment difference), 95% confidence interval for the difference, p-value, and effect size will be reported for each derived visit.

Subgroup analyses by ADHD subtype (see Section 4.4.1) will be performed for select secondary efficacy variables. No multiplicity correction to the reported p-values will be made for any secondary efficacy analysis. Supportive analyses of secondary efficacy endpoints may be performed using the PP analysis set.

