6 CHANGES TO PLANNED ANALYSES

6.1 Changes to analyses specified in protocol

Not applicable.

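### SAP 5.4 gives no model-based treatment comparison for ADHD-RS-5 remission (total score ≤18), although the objectives call for one and the other two remission criteria are modelled

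*SAP*

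**What the plan says.** **Objective.** SAP 2.1.2 states the aim as a comparison: "To evaluate AEVI-001 compared with placebo on remission at Visit 8/ET (Week 6/ET), based on the following parameters". Protocol Section 7 and the synopsis have the same objective. Three criteria follow, and the first is "An ADHD-RS-5 total score ≤18". The others are a CGI-I of 1, and both conditions together.

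**Derivation.** SAP 4.7.1.3 builds the endpoint variable: "In addition to deriving ADHD-RS-5 remission at each timepoint, an LOCF ADHD-RS-5 remission indicator will be calculated". SAP 4.7.2.2 and 4.7.3.2 do the same for CGI-I remission and combined remission.

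**Analysis.** SAP 5.4 opens with one model: "Logistic regression methods will be used for the analysis of the LOCF ADHD-RS-5 response indicator using the full analysis set". It then extends the method: "Similar logistic regression models will be used for the LOCF CGI-I remission, LOCF combined ADHD-RS-5/CGI-I response, and LOCF combined ADHD-RS-5/CGI-I remission indicators". A covariate sentence follows: "For the CGI-I response/remission analyses, baseline CGI-S score will be included in the model". Another assigns both baseline scores to the combined endpoints. None of these sentences names ADHD-RS-5 remission.

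**What ADHD-RS-5 remission does receive.** The end of SAP 5.4 provides descriptive summaries of the response and remission indicators by arm and derived visit.

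**Protocol statistics text.** Protocol 14.1.1 says response and remission are to be presented as percentages. Protocol 14.3.4 adds: "Comparisons of dichotomized responses between treatment groups will be based on odds ratios and associated 95% CIs resulting from the logistic regression model". SAP 6.1, on changes from the protocol, reads "Not applicable".

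**The concern.** An objective worded as a comparison with placebo normally leads to an estimated treatment effect with its uncertainty. Two of the three remission criteria get that and the third does not, and the SAP gives no reason.

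The omitted criterion is the only one of the three that rests on the primary scale alone. Combined remission adds a CGI-I condition to it, so the plan models the narrower endpoint and leaves the broader one to a table of percentages.

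SAP Section 1 requires the plan to be final before database lock and unblinding. If the gap is noticed only when the tables are read, any adjusted comparison on this criterion will be post hoc.

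**Working it through.** **1. The plan's own figure.** The documents give no rate or power for remission. The only stated Part A figure is about 80% power for the primary endpoint, with about 34 subjects providing data, effect size 1.0 and two-sided α = 0.05 (SAP 2.3). With 34/2 = 17 per arm, the two-sample t-test has noncentrality 1.0 × √(17/2) = 2.92 on 32 degrees of freedom. Power is 80.7%, so the figure is reproduced. The present point does not depend on it.

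**2. Criteria against models.**

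| Remission criterion | In the comparative objective | LOCF indicator | Logistic model in SAP 5.4 |
|---|---|---|---|
| ADHD-RS-5 ≤18 | yes | SAP 4.7.1.3 | none |
| CGI-I = 1 | yes | SAP 4.7.2.2 | yes |
| Both | yes | SAP 4.7.3.2 | yes |

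Three are stated, three derived and two modelled. No model in SAP Section 5 uses the LOCF ADHD-RS-5 remission indicator.

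**3. Does the combined model cover it?** No. Combined remission requires a score ≤18 and also a CGI-I of 1. Both scales are scheduled at every visit from 3 to 8/ET. When the two scores come from the same visit, every combined remitter is an ADHD-RS-5 remitter, so combined remission cannot be the more frequent of the two in either arm. Subjects who reach ≤18 without a CGI-I of 1 count as failures in the combined model.

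**4. Does the ADHD-RS-5 response model cover it?** No. Entry requires a baseline score of at least 28 and the scale maximum is 54. The reduction needed to reach 18 is (baseline − 18)/baseline:

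- baseline 28: (28 − 18)/28 = 10/28 = 35.7%
- baseline 40: (40 − 18)/40 = 22/40 = 55.0%
- baseline 54: (54 − 18)/54 = 36/54 = 66.7%

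Response needs 30% at any baseline. Remission is therefore stricter everywhere, and the gap widens with baseline severity. A subject who falls from 40 to 28 has a 12/40 = 30% reduction and is a responder, but is 10 points short of remission.

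**5. Does another sentence bring it in?** The covariate sentences in SAP 5.4 cover CGI-I endpoints and combined endpoints. The first of them mentions CGI-I response, which the model list also leaves out. That suggests the list is incomplete by oversight. CGI-I response is a different endpoint, and restoring it would not restore ADHD-RS-5 remission.

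**The case against.** Several parts of the case against this point stand.

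- **The endpoint is still reported.** SAP 4.7 gives LOCF variables their own derived visit label, so the end-of-treatment percentages will be tabulated by arm. SAP Section 5 allows 95% CIs on descriptive statistics where appropriate. A reader might infer that the remission question cannot be answered on this criterion. That goes too far: what is missing is the adjusted odds ratio with its CI and p-value.
- **The protocol does not plainly require the model.** Protocol 14.1.1 promises percentages, and the logistic sentence in 14.3.4 speaks of dichotomized responses, following text about responder status. A reader might take the entry in SAP 6.1 as concealing a departure from the protocol. The documents do not support that, because no protocol sentence explicitly assigns a logistic model to remission.
- **Relative frequency is only partly known.** It is tempting to say that both modelled criteria are rarer than the omitted one. That follows for combined remission, in the sense of no more frequent. Nothing in the documents shows that a CGI-I of 1 is rarer than a score ≤18.
- **A power contrast would rest on assumptions.** Take 17 per arm, SD of change 10, an arm difference of 10, baseline mean 36 to 40 with entry at 28, and placebo change −6 to −14. ADHD-RS-5 remission then has about 36–54% power in an unadjusted two-proportion test. Combined remission has about 10–20% if 30–50% of remitters also have a CGI-I of 1, but about 27–40% if 80% do. ADHD-RS-5 response, which is modelled, has roughly 60% at placebo changes of −6 or −10. Apart from the 17 per arm, the entry score and the effect size of 1.0 behind the arm difference, none of these inputs is in the documents. They do not support calling the omitted criterion the most informative one.
- **The stakes are modest.** This is one additional secondary endpoint in a Phase 2 trial, without multiplicity correction and outside the fixed testing sequence.

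None of this explains why two of three parallel criteria are modelled and the third is not.

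**Conclusion.** The point holds as an inconsistency between the comparative remission objective, the three derived indicators and the two models in SAP 5.4. Followed as written, the Part A plan yields by-arm percentages for ADHD-RS-5 remission, with optional CIs, and no adjusted treatment comparison. Its subset, combined remission, is modelled. The response model does not fill the gap, because remission needs a reduction of between 35.7% and 66.7%, depending on baseline.

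The size is one missing secondary comparison out of three on remission. The conclusion rests on the text and on the entry score of 28, and on no assumed remission rate. The primary analysis, its alpha and the sample size are not affected. It is worth correcting before lock because a later correction would be post hoc.

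**What to change.** In SAP 5.4, add LOCF ADHD-RS-5 remission to the list of indicators analysed by logistic regression. Use the model already specified for ADHD-RS-5 response, with baseline ADHD-RS-5 total score, age stratum and treatment as terms, on the full analysis set. Report the odds ratio, its 95% CI and the p-value.

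If the sponsor intends this criterion to be descriptive only, the SAP should say so, give the reason, and reconcile that with the comparative objective in 2.1.2.

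The cost is one phrase and one further model on an indicator that is already derived. The drawback is one more secondary p-value, uncorrected like the others in SAP 5.4. The change should be made before database lock and unblinding. The same edit is a convenient time to check the list for CGI-I response, which needs its own entry.

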5.5 Safety analyses

For all safety endpoints, descriptive statistics will be presented by treatment group and visit (where applicable) using the safety analysis set. In addition, some safety endpoints may be further summarized by optimized dose (see Section 4.6). In summaries of change from baseline safety variables, only subjects with both baseline and post baseline data will be included. No formal hypothesis tests will be performed for any safety endpoint.

5.5.1 Concomitant medications and study drug exposure

5.5.1.1 Concomitant medications

The incidence of concomitant medication use will be summarized by treatment group and preferred term (see Section 4.5 for definition of concomitant medications). Each concomitant medication reported more than one time will only be counted once per subject for each preferred term. All concomitant medication data will be listed by subject.

5.5.1.2 Study drug exposure

Optimized dose, total study drug exposure, and duration of total exposure will be summarized by treatment group. All study drug exposure data will be listed by subject.

5.5.1.3 Study drug compliance

Overall percent compliance will be summarized by treatment group. In addition, the frequency and percentage of subjects in each compliance category (see Section 4.6 for definition of overall compliance indicator) will be tabulated by treatment group. All compliance data will be listed by subject.

5.5.2 AEs

The overall incidence of subjects having at least one AE in each of the following categories will be summarized by treatment group:

- Any TEAE
- Any SAE
- Any AE leading to death
- Any TEAE leading to study drug withdrawal
- Any related TEAE

All AE data will be listed by subject. Separate listings by subject will presented for all SAEs, AEs leading to death, and TEAEs leading to study drug withdrawal.

5.5.2.1 TEAEs

The incidence of TEAEs will be summarized by treatment group, system organ class (SOC), and preferred term. Each subject will be counted only once per SOC and preferred term. An additional display may be produced by treatment group and preferred term.

5.5.2.2 SAEs

The incidence of SAEs will be summarized by treatment group, SOC, and preferred term. Each subject will be counted only once per SOC and preferred term.

5.5.2.3 TEAEs leading to study drug withdrawal

The incidence of TEAEs leading to study drug withdrawal will be summarized by treatment group, SOC, and preferred term. Each subject will be counted only once per SOC and preferred term.

5.5.2.4 TEAEs by maximum relationship to study drug

The incidence of TEAEs will be summarized by maximum relationship to study drug, treatment group, SOC, and preferred term. Each subject is counted only once per preferred term and most related category reported.

5.5.2.5 TEAEs by maximum severity

The incidence of TEAEs will be summarized by maximum severity to study drug, treatment group, SOC, and preferred term. Each subject is counted only once per preferred term and most severe category reported.

5.5.3 Laboratory test results

Descriptive statistics for all reported values and change from baseline values will be summarized by test category, treatment group, and visit. Only the original assessment for each visit will contribute to descriptive statistics; repeat or unscheduled assessments will not be included in the calculation of descriptive statistics by visit. All laboratory test

results data (including pregnancy test and urine drug screen data and any repeat or unscheduled assessments) will be listed by subject and visit.

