# 6.2 Clinical Experience

Previously, AEVI-001 was in phase 3 development for adults with cerebrovascular diseases and dementia. The previous sponsor (Nippon Shinyaku Co., Ltd.) performed the following studies:

- ☐ Phase 1 tolerability, dose-finding and pharmacokinetic study in healthy volunteers.
- Phase 2 studies in subjects with residual symptoms following cerebral infarct or cerebral hemorrhage.
- ☐ Phase 3 study in subjects with cerebrovascular diseases and dementia.

Exposure to AEVI-001 in these studies is presented in Table 2.

Table 2: Nippon Shinyaku Co., Ltd. Conducted Clinical Studies with AEVI-001a

Study Phase	Study Population	Number of Subjects	Doses Tested	Exposure	Number of Treatment- related SAEs
1	Healthy male adults	30/6 b	25-800 mg single dose/ 200 mg/day	8 days	0
2	Adults with cerebrovascular disease	169	75-450 mg/day	8 weeks	0
2	Adults with post cerebral infarct residual symptoms	288	150 and 300 mg/day	8 weeks	0
3	Adults with cerebrovascular disease and dementia	Not available	300 mg/day	6 months to 1 year	2°

Abbreviation: SAE = serious adverse event

- a Previously referred to as NS-105.
- b A total of 30 subjects were involved in dose finding at 25 800 mg, a further 6 subjects were tested at the recommended dose obtained during dose finding (200 mg).
- Relationship to study treatment was categorized as unknown. One subject experience acute myocardial infarction and one subject was hospitalized for vertigo and vomiting.

Nippon Shinyaku terminated development because the phase 3 study in adults with cerebrovascular disease and dementia failed to meet the defined efficacy endpoints. Although a written report is unavailable, information in the Investigator's Brochure (IB) for this phase 3 study indicated that AEVI-001 was well-tolerated over 8 weeks of continuous daily dosing at doses up to 450 mg/day. The most frequently reported adverse events (AEs) were nausea (2% of subjects)

and laboratory abnormalities including elevated liver function tests, including alanine aminotransferase, aspartate aminotransferase, and alkaline phosphatase (in 3% of the subjects each), and elevated creatine kinase (in 1% of the subjects).

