### 14.1.2 Safety

Adverse events will be coded using the most recent version of the Medical Dictionary for Regulatory Affairs and will be summarized by system organ class (SOC) and preferred term. by system organ class and preferred term. Adverse events will be analyzed by frequency, severity, relationship to IP, and their effect on participation in the study.

Clinical laboratory values will be compared to normal ranges and flagged for levels of clinical concern. The analysis will focus on the frequencies of abnormal values as well as within-subject changes observed during the study.

Vital signs and ECG recordings will also be examined for changes during the study that may be attributed to exposure to IP.

The C-SSRS will also be examined for changes that may be attributed to exposure to IP.

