### 14.3.5.2 Clinical Laboratory Evaluations

Descriptive summaries for all reported values and change from baseline values will be summarized by laboratory test category, treatment group, and visit.

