4.8.2 Laboratory test results

Blood and urine samples will be collected by site staff for clinical laboratory testing. Urine pregnancy tests will be performed at the site. All other samples will be analyzed at the central laboratory. For all samples collected, the following data will be recorded in the eCRF: test category (i.e., Hematology, Serum Chemistry, Urinalysis, Serum Pregnancy Test, Urine Pregnancy Test, or Urine Drug Screen), collection date, and the accession number. For urine pregnancy tests, the result will also be recorded in the eCRF as "POSITIVE" or "NEGATIVE".

Collected laboratory samples will then be processed at the central laboratory for the calculation of reported values for the laboratory tests shown in Table 3. Central laboratory data will include test category, lab test name, reported result, reported unit, reported reference range (i.e., low and high), International System of Units (SI) result, SI unit, SI reference range, and reference range indicator. The reference range indicator will be recorded as "NORMAL" or "ABNORMAL" for character results and as "NORMAL", "LOW", or "HIGH" for numeric results. Data from the central laboratory will be combined with the laboratory eCRF data prior to analysis.

Change from baseline values to each post-baseline assessment will be calculated for all continuous laboratory tests.

Test category	Tests assessed
Hematology	hemoglobin, hematocrit, red blood cell count, red blood cell indices, mean corpuscular hemoglobin, mean corpuscular hemoglobin concentration, mean corpuscular volume, platelet count (or estimate), white blood cell count including differential
Serum chemistry	albumin, total bilirubin, total protein, calcium, alkaline phosphatase, alanine aminotransferase, aspartate aminotransferase, blood urea nitrogen, creatinine, creatine kinase, glucose, sodium, potassium, chloride, bicarbonate, lactate dehydrogenase, uric acid, thyroid stimulating hormone ¹ , T4 ¹
Urinalysis	pH, specific gravity, blood, glucose, protein, ketones
Pregnancy test ²	serum, urine
Urine drug screen	amphetamines, barbiturates, benzodiazepines, cocaine, opiates, phencyclidine, cannabinoids, propoxyphene, methadone

Table 3: Laboratory test categories and tests assessed

¹ Screening only

² Females only

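### Protocol 14.1.2 names frequencies of abnormal laboratory values as a focus, but SAP 5.5.3 plans no such count, so out-of-range results not reported as adverse events are listed and never counted by arm

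*SAP*

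**What the plan says.** The protocol describes the laboratory analysis in more than one place, and the accounts differ.

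- **Protocol 14.1.2 (Safety, under Study Endpoints):** "Clinical laboratory values will be compared to normal ranges and flagged for levels of clinical concern". It continues: "The analysis will focus on the frequencies of abnormal values as well as within-subject changes observed during the study".
- **Protocol 14.3.5.2 (the laboratory part of the safety analyses) reads:** "Descriptive summaries for all reported values and change from baseline values will be summarized by laboratory test category, treatment group, and visit". Frequencies of abnormal values are not mentioned. The synopsis, under Safety Analyses, likewise speaks only of descriptive statistics by visit.

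The SAP, which covers Part A only, follows the second account.

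- **SAP 5.5.3:** "Descriptive statistics for all reported values and change from baseline values will be summarized by test category, treatment group, and visit". It restricts these to the original assessment at each visit: "repeat or unscheduled assessments will not be included in the calculation of descriptive statistics by visit". All results, including repeat and unscheduled ones, go to listings by subject and visit.
- **SAP 4.8.2:** the central laboratory data carry a reference range indicator for each result: normal, low or high for numeric results, and normal or abnormal for character results. No table in 5.5.3 uses it.
- **SAP 6.1 (changes to the analyses specified in the protocol):** "Not applicable".
- **SAP 5.5.4 and 5.5.5:** vital signs and ECG get counts and percentages, by arm, of subjects with potentially clinically important values. ECG also gets counts of abnormal findings. Both sections state that repeat and unscheduled assessments are included.

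**The concern.** Protocol 14.1.2 puts the frequency of abnormal values at the centre of the laboratory analysis. The SAP plans no such frequency and does not say that it was left out. Of the three groups of objective safety measurements, laboratory tests are the only one with no abnormal-value count by arm.

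A laboratory effect may show as a few subjects leaving the reference range rather than as a shift in the mean. Summaries of values and changes at each visit describe the distribution. They do not say how many subjects in each arm were ever out of range, or how many moved out of range after starting treatment. A value found at a repeat or unscheduled draw is not in those summaries at all. No data monitoring committee is planned (Protocol 13), so the final tables are the planned comparison of laboratory safety between arms.

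**Working it through.** The plan states no figure on this point, so the check is mainly a comparison of text.

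**1. What each section delivers for laboratory tests**

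| Element | Protocol 14.1.2 | Protocol 14.3.5.2 | SAP 5.5.3 |
|---|---|---|---|
| Change from baseline | yes | yes | yes |
| Comparison with normal ranges, flagging | yes | not mentioned | not tabulated |
| Frequency of abnormal values | yes | not mentioned | no |
| Repeat and unscheduled results | not addressed | not addressed | listings only |

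The two protocol sections are compatible, since 14.3.5.2 does not rule out frequencies. The SAP implements 14.3.5.2 in nearly the same words and leaves the rest of 14.1.2 undone.

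**2. Comparison with the neighbouring SAP sections**

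SAP 5.5.4 and 5.5.5 open as 5.5.3 does and then add counts of subjects by arm over all assessments. For vital signs, the protocol's analysis section (14.3.5.3) asks only for descriptive statistics, so the SAP added counts that this section does not name. For laboratory tests it omitted counts that Protocol 14.1.2 does name.

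**3. Where an out-of-range result goes under the current plan**

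- Judged clinically relevant by the investigator: reported as an adverse event (Protocol 10.3.3.1) and, if treatment-emergent, tabulated by arm (SAP 5.5.2.1).
- Not so judged, original scheduled assessment: enters the by-visit mean, SD, median, minimum and maximum (SAP 5) and the listing. It is not counted as out of range.
- Not so judged, repeat or unscheduled: listing only.

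The uncounted group is therefore the second and third rows. The documents give no rate for it.

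**4. Background that a simple count would pick up**

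Inputs: hematology and chemistry are drawn after dosing at Visits 3, 6 and 8 (Schedule of Events), so three scheduled samples. Part A randomizes 42 subjects 1:1, so 21 per arm, or 64/2 = 32 if enlarged. Assumption: the reference range covers 95% of values when there is no drug effect.

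- Samples independent: P(any out of range) = 1 − 0.95³ = 1 − 0.857 = 0.143, or about 14% per test. Expected subjects: 0.143 × 21 = 3.0, or 0.143 × 32 = 4.6.
- Samples perfectly correlated within a subject: 5%. Expected subjects: 0.05 × 21 = 1.1, or 0.05 × 32 = 1.6.
- In range at baseline and out of range later: 0.95 × 0.143 = 0.135 under independence, and 0 under perfect correlation.

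So chance alone gives roughly 1 to 3 subjects per test in an arm of 21. Baseline status removes subjects who are persistently out of range. It removes little of the purely random part, for which the placebo arm is the reference.

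**The case against.** The strongest case against is that the SAP did follow the protocol. Protocol 14.1.2 sits under endpoints, 14.3.5.2 is the analysis section, the synopsis agrees with 14.3.5.2, and SAP 5.5.3 repeats it closely. This stands in part. A reader might infer that the SAP dropped the protocol's one stated laboratory analysis. The documents do not support that, because the protocol contains two statements. They do show an unimplemented commitment and an inconsistency that SAP 6.1 leaves unmentioned.

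A reader might also infer that liver-enzyme elevations go uncounted or disappear from the report. That is too strong. Changes judged clinically relevant enter the adverse event tables by arm, SAP 5 includes the minimum and maximum so a scheduled outlier would be visible, and every result is listed. What remains true is that a maximum does not say how many subjects were abnormal, a listing does not compare arms, and adverse event capture rests on the investigator's opinion, whereas 14.1.2 refers to normal ranges.

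It is tempting to size the loss from Protocol 6.2, which reports raised liver enzymes in 3% of subjects each. That figure cannot carry the weight. It is an adverse event frequency from adults with cerebrovascular disease and dementia, from a study without an available written report, and with no comparator rate. It does not establish a drug effect. Events recorded as adverse events are also the ones this plan would already count by arm.

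SAP 5 says that categorical data receive frequencies and percentages. That could cover character results such as urinalysis at each visit. It does not name the range indicator, and 5.5.3 does not call for it.

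Finally, a low or high flag is a looser standard than a level of clinical concern, and the protocol promises no shift table. Both statements are correct, and the fix should allow for them.

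**Conclusion.** The point holds in a limited form. The protocol gives two accounts of the laboratory analysis. The SAP implements the narrower one, with original visit assessments only, and records no departure. Out-of-range laboratory values not reported as adverse events are therefore listed but not counted by arm, and repeat and unscheduled values reach no laboratory summary table.

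The size of the loss cannot be stated from the documents. Efficacy results, the sample size and the type I error rate are untouched, and no formal safety tests are planned (SAP 5.5). What suffers is the descriptive comparison of laboratory safety between arms, which is weaker than Protocol 14.1.2 describes and weaker than what the SAP gives vital signs and ECG. The conclusion rests on the text alone. The background range of 5% to 14% per test rests on the assumed 95% reference ranges and on three post-dose samples that lie between perfectly correlated and independent.

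**What to change.** In SAP 5.5.3, add a table by arm and test giving the number and percentage of subjects with any post-dose low or high value (abnormal, for character results). Use the reference range indicator from SAP 4.8.2 and include repeat and unscheduled results, as 5.5.4 and 5.5.5 already do. Show it against baseline status, for example as a shift from baseline to the worst post-dose category with low and high kept separate, so that newly abnormal values are distinguished from those already present.

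Reconcile Protocol 14.1.2 with 14.3.5.2. Say whether the reference range indicator is what 14.1.2 means by flagging for clinical concern, since no separate laboratory criterion is defined. If the sponsor prefers not to tabulate frequencies, SAP 6.1 should state and justify that departure.

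This is a cheap improvement: a little more programming from data already planned, with no effect on sample size, alpha or blinding. The downside is that some trivial out-of-range values will be counted, about 14% of subjects per test by chance under the independence assumption above, so the table should be read as a comparison with placebo.
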